# A.2. Aim 2: Systematic Review and Synthesis of the Evidence Outcome Measures

The quality of the studies will be evaluated using the Cochrane Criteria List for Methodological Quality Assessment. Finally, evidence will be summarized and interpreted, to guide the development of the DA. Results will be reviewed via focus groups by the *expert working group*, to confirm accuracy and credibility.

# A.3. Aim 3: Alpha Testing with the Expert Working Group Outcome Measures

The DA will be presented to the *expert working group*, and feedback on the accuracy, comprehensibility, and usability of the DA prototype will be collected. This study will use descriptive statistics for evaluating accuracy, comprehensibility, and usability of the DA. **Accuracy** of the DA will be determined by the percentage of *expert working group* members who perceive the presented risks and benefits in the DA to align with the scientific evidence available on the prosthetic design decision outcomes. **Comprehensibility** of the DA will be classified as the degree to which the DA content covers information necessary for making an informed decision about prosthetic design, and will be evaluated using a Likert scale for each component of the DA. **Usability** will be qualified as the extent to which the information presented in the DA is clear, understandable, and effective, and will be evaluated using a Likert scale for each component of the DA. Additional feedback on the accuracy, comprehensibility, and usability of the DA prototype will be collected by means of short individual semi-structured interviews after each round of alpha testing.

# B. Description of Population to be Enrolled:

## B.1. Aim 1-3: Assemble an expert working group

A separate **expert working group** will be assembled for consultation throughout all aims of the proposed work, and for alpha testing in *Aim 3*. In order to check the credibility of results and ensure all appropriate topics necessary for prosthetic design decision making are included in an initial DA prototype, focus groups will be conducted with the expert working group to review and confirm the results from *Aims 1 and 2*. In order to alpha test the DA prototype in *Aim 3*, quantitative data and semi-structured individual interviews will be conducted with the expert working group.

The *expert working group* will consist of at least 5 and up to 12 people with LLA actively receiving prosthetic care, and at least 5 and up to 12 prosthetic care providers with greater than 5 years of experience. Individuals will be invited to join the *expert working group* based on expertise, and representation of key stakeholders relevant to the prosthetic design process identified in *Aim 1* (e.g., certified prosthetists, therapists, physicians, and other caregivers). Patient expert group members will be identified through the University of Colorado Health Amputee Support Group, through the Amputee Coalition of America, and through Amputee List Serve (AMP-L). Healthcare provider expert group members will be identified through local and professional clinic partners and the Orthotics and Prosthetics List Serve. The group will be referred to for checking credibility of results, in the development and refining process of the DA, and alpha testing

# B.2. Aim 1: Qualitative Study Participants and Sampling Plan

Participants (estimated up to 14 patients, within 1 year from lower limb amputation, receiving their first prosthesis and up to 24 prosthetic care providers) will be recruited through well-established clinical partners representing diverse prosthetic practice environments (including the Denver VA Medical Center and private prosthetics practices), located in Albuquerque, NM, Tucson, AZ, and Denver, CO, and clinics throughout the US. Patient participants will also be recruited through the Amputee Coalition of America, and through Amputee List Serve (AMP-L). Standard to qualitative research methods, purposive sampling will be employed to ensure maximum variation of socio-demographic and clinical characteristics, and to ensure inclusion of all key stakeholders in the prosthetic design process.65 Prosthetic care providers will be sampled based on a diverse representation of professional experience and involvement in the prosthetic design process, including prosthetists, therapists, physicians, and associated care providers. Patient participants will be sampled based on diverse representation of above- and belowknee amputation, age, sex, etiology, and availability to participate in a 1-hour, semistructured interview. The patient sample is expected to reflect a distribution of amputation levels and etiologies similar to population-level estimates: ~54% vascular and ~45% traumatic etiology. 66 Patients will be recruited early in their rehabilitation process, for insight into the decisional needs for their first prosthesis and initial care planning. Recruitment will target 14 patients and 24 prosthetic care providers with the goal of achieving thematic saturation, the point where no additional properties of themes emerge from qualitative analysis. 67-69 If thematic saturation has not been attained, enrollment will continue beyond the targets for each group.

## C. Study Design and Research Methods

# C.1. Overview of Approach

The goal of this proposal is to develop and conduct alpha testing of a DA for prosthetic design decisions. The aims in this proposal are guided by IPDAS for developing patient decision aids (**Figure 2**).

[figure not shown]

Figure 2: Steps for development of a DA, adapted from the International Patient Decision Aids guidelines, Coulter et al. 63

Steps will include **Aim 1**) qualitatively define the scope and purpose of the DA; **Aim 2**) review and synthesize the available evidence to inform the development of a prosthetic design DA prototype; and **Aim 3**) alpha testing for accuracy, comprehensibility, and usability of the DA, with an expert group of patients and prosthetic care providers. **Aims 1** and **2** are an exploratory sequential mixed methods study design for developing the DA, a commonly used study design for instrument development. **Aim 3** is a convergent parallel mixed method design for alpha testing of the DA. **(Figure 3)** 

[figure not shown]

Figure 3: Study design overview

# C.2. Aim 1: Define the Scope and Purpose of the DA

The objective of *Aim 1* is to qualitatively define the scope and purpose of the DA, by exploring the key determinants for prosthetic design decisions, and decisional needs of both patients and prosthetic care providers during prosthetic design. This aim will clarify 1) all components of prosthetic design decisions that will be included in the DA prototype, 2) the key determinants that contribute to decision making, 3) the target end users of the DA, and 4) the necessary content to be included in the DA that will help inform the decision.

# C.3. Aim 2: Review the Evidence for Prosthetic Design Decision Options to Develop a DA Prototype.

The purpose of **Aim 2** will be to develop a DA prototype for new prosthetic users over two steps: 1) systematic review of the evidence on the prosthetic design decision options identified in **Aim 1** and their associated risks and benefits; and 2) development of a DA prototype.

# C.3.1. Aim 2: Systematic Review and Synthesis of the Evidence on Prosthetic Design Decision Options

A comprehensive systematic literature review will be conducted on the relevant data and evidence associated with the available options, as they relate to the key components of prosthetic design decisions and the decisional needs defined in *Aim 1*. The review will appraise the available evidence on the risks and benefits of the possible choices associated with each component of prosthetic design, and summarize the results in a final document. The systematic review will follow the Cochrane Handbook and PRISMA Guidelines for Systematic Reviews.

# C.3.2. Aim 2: Developing a DA Prototype

The development of the DA proposed in this study will follow the IPDAS guidelines for decision aid development. Based on this guideline, the DA will include high quality evidence on the options in sufficient detail for each decision associated with prosthetic design, potential outcome probabilities, clarity for identifying patient values associated with each option, and guidance on deliberation and communication. Use of plain language will be implemented and checked by the *expert working group*, for comprehensiveness for all literacy levels. Format of the decision aid will be established (i.e., paper article, video, web-based). For accessibility in multiple environments (long distance vs. local, internet access vs. no technology access), a minimum of two formats will be considered.

# C.4. Aim 3: Assess the Accuracy, Comprehensibility, and Usability of the DA Through Alpha Testing with the **Expert Working Group** of Patients and Associated Healthcare Providers.

The objective of this aim is to assess the accuracy, comprehensibility, and usability of

the DA through alpha testing with an **expert working group** established in *Aim 1*. The DA will be presented to the **expert working group**, and feedback on the accuracy, comprehensibility, and usability of the DA prototype will be collected. Evaluating the accuracy, comprehensibility, and usability of the DA with potential end-users will ensure that 1) the DA contains high quality accurate information, 2) the DA presents material that is valuable to the decision making process for prosthetic design, and 3) the DA is logical and understandable to the target end users, and can be feasibly and rapidly adopted in practice.  Both qualitative and quantitative data will be collected and analyzed separately, to create a more complete understanding of the DA's accuracy, comprehensibility, and usability.  The alpha testing will inform iterative modifications to the DA in future prototypes, and will produce findings that will determine whether the DA should be recommended for pilot testing in the clinic setting. 

# D. Description, Risks and Justification of Procedures and Data Collection Tools:

The risks associated with the semi-structured interviews are minimal. Additionally, the quantitative measures to be used (e.g., questionnaires) are low-risk and considered to be safe. These minimal and low-risks include the risk of misinterpretation of discussion and questionnaires, potentially resulting in negative or unproductive thoughts by the patient or prosthetist. Additionally, one purpose of the semi-structured interviews is to uncover any unforeseen consequences of the information included in DA (e.g., patient anxiety about prosthetic decisions, recovery) and to address these risks. It is also important to note that patients and therapists already discuss prosthetics and prognosis as part of standard care, however currently these discussions are woefully under-informed by evidence. Finally, rare, unknown, or unforeseeable (unexpected) risks may also occur.

As with all clinical research studies, there is the general risk of breach of confidentiality or data security. To minimize this risk, only the minimal necessary data will be collected, and procedures to maintain confidentiality will be followed.

Little research has been conducted to promote shared decision making as a method for improving patient outcomes for people with LLA. This study will initiate work on developing a DA prototype to identify the potential for efficacy and implementation in clinical practice. The patient and clinician participants have potential to benefit immediately from the educational experience surrounding interaction with research team who are highly interested in addressing functional limitations and disability following non-traumatic lower-limb amputation. In addition, the results of the study will indicate whether larger efforts (i.e., Phase II trial) are indicated to test implementation of such intervention as a key element of standard prosthetic design decisions following LLA.

#### E. Potential Scientific Problems:

Due to the pilot design of the proposed study, and to maximize successful use of DA, we have selected optimal champion clinic partners for our initial *Aim 1* qualitative exploration and for the **expert working group**. Participant selection will be, in part, based on their willingness participate in feedback on incorporating novel measures into practice, which may introduce limitations in generalizability and bias around future DA implementation in other clinics. Therefore, data collection and recruited participants will be a convenience sample, which may introduce limitations in generalizability and bias around future DA testing in other clinics.

## F. Data Analysis Plan:

## F.1. Aim 1: Qualitative Data Analysis

Transcripts from the semi-structured interviews and focus groups will be analyzed with ATLAS.ti 7.0 software using qualitative directed content analysis. 75,76 Qualitative directed content analysis is a process where existing theory guides the discussion and interpretation of the research findings, providing focus for the research question, to produce a final identification of themes, patterns, or categories. Pre-determined codes will be based on steps of SDM defined by the Shared Decision Making Model for Clinical Practice, 10 and on existing theory of decisional needs, as described by the Ottawa Decision Support Framework. In order to maintain inter-coder reliability, two members of the research team (one clinician and one non-clinician, to manage potential biases) will independently review and code the transcripts, and reconcile results. Codes will be modified or added as needed; any new material that does not fit with existing codes will be discussed to further extend or refine the existing decisional needs. In the circumstance of any disagreements, a third team member will consult. Codes will then be grouped into themes to identify the primary components of prosthetic design decisions, determine the key determinants for each decision, and identify the decisional needs of both patients and prosthetic care providers. To maintain unbiased results and trustworthiness of the findings, coding rules and an audit process will be used. 76 Credibility of results will be ensured by conducting focus groups to share and evaluate the final themes with an established expert working group of prosthetic care providers and patients with LLA (described below). In order to develop a DA prototype in Aim 2, this aim will clarify the primary decisions and identify the key decisional needs (e.g., knowledge needs of patients and healthcare providers, associated values). Results from this aim will be foundational for defining current SDM practices in prosthetic design, identifying areas of need for decision support, identifying end users of the DA, and informing a SDM training and implementation strategy in future pilot work.

#### F.2. Aim 2: Systematic Review Analysis

The systematic review will follow the Cochrane Handbook and PRISMA Guidelines for Systematic Reviews. 61,72 Two study reviewers will identify relevant work from multiple resources (e.g., MEDLINE, EMBASE). Key search terms and inclusion criteria will be established prior to searching for identifying relevant work (e.g., pertaining to LLA participants, inclusion of outcomes of interest, key words reflective of the decisional needs identified in *Aim 1*). The quality of the studies will be evaluated using the Cochrane Criteria List for Methodological Quality Assessment. 61 Finally, evidence will be summarized and interpreted, to guide the development of the DA. Results will be reviewed via focus groups by the *expert working group*, to confirm accuracy and credibility. 6

# F.3. Aim 3: Alpha Testing and Iterative Modification With the Expert Working Group

The DA will be presented to the *expert working group*, and feedback on the accuracy, comprehensibility, and usability of the DA prototype will be collected. All quantitative data will be collected through Research Electronic Data Capture (REDCap) and analyzed with R, version 3.5.1. This study will use descriptive statistics for evaluating accuracy, comprehensibility, and usability of the DA. Based on thresholds in published testing of accuracy, comprehensibility, and usability of existing DAs, 80% will be the threshold for each component of the prosthetic design decision included in the DA. If accuracy, comprehensibility, and usability score less than 80%, the DA will be revised and an additional round of alpha testing will be conducted. Iterative revisions to the DA and rounds of alpha testing will continue until all outcomes measure 80% or greater.

Additional feedback on the accuracy, comprehensibility, and usability of the DA

prototype will be collected by means of short individual semi-structured interviews after each round of alpha testing. Results from the qualitative feedback on the DA prototype will inform revisions to the prototype for additional rounds of alpha testing, and inform an implementation plan for future clinical use of the DA, including training on SDM in prosthetic care. Thematic analysis will be used to analyze results from the *Aim 3* qualitative interviews. An initial coding team of 3 researchers will develop the code book for each group of interviews (patients and prosthetic care providers), and once agreement is established (estimated 3-6 interviews), remaining transcripts will be coded by two primary coders. The coding team will include both clinical and non-clinical members to minimize potential bias (e.g., prosthetist, occupational therapist, and non-clinical research assistant). All transcripts will be coded and analyzed via open coding using Atlas.ti software. Methods for maintaining trustworthiness and credibility will reflect those listed in **Aim 1**.

Finally, in the convergent mixed methods design, qualitative and quantitative data from **Aim 3** will be individually analyzed and then consolidated to explain any unanswered questions or unexpected findings in the alpha testing of the DA. Common concepts will be integrated and compared to identify and describe feasibility and acceptability results, using data consolidation and merging. Data connection methods will be used to maximize strengths and minimize weaknesses of both qualitative and quantitative results. Results from the analysis will further improve and tailor the DA to fit the need of both patients and prosthetic care providers, and inform study procedures and implementation methods for pilot testing in a clinical beta testing trial. Modifications will be made to the DA in an iterative process (at least two rounds of testing and modification with the **expert working group**, or until greater than 80% DA accuracy, comprehensibility, and usability is achieved) to ensure that the DA is optimal for clinical implementation. An audit trail will be maintained through the modification process, for reporting feedback and how this feedback was incorporated into the design.

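### F.3 states the rule for ending alpha testing in two forms that do not agree, and reporting accuracy by group would show what a pooled 80% can hide

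*Combined protocol and SAP*

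**What the plan says.** **Stopping rule.** F.3 sets the target: "80% will be the threshold for each component of the prosthetic design decision included in the DA". It calls for revision and another round when scores fall below 80%, and adds: "Iterative revisions to the DA and rounds of alpha testing will continue until all outcomes measure 80% or greater". The closing paragraph of F.3, on mixed-methods integration, describes the same process differently. There the iteration runs for a minimum of two rounds with the expert working group, or until the three scores are strictly above 80%.

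**Who is scored.** A.3 scores accuracy over the whole expert working group, as the share of "members who perceive the presented risks and benefits in the DA to align with the scientific evidence available on the prosthetic design decision outcomes". Comprehensibility and usability each "will be evaluated using a Likert scale for each component of the DA"; neither the denominator nor the conversion from rating to percentage is given. B.1 sets the make-up of the group. On the patient side it asks for "at least 5 and up to 12 people with LLA actively receiving prosthetic care". The provider side has the same size limits, and its members must have more than five years' experience.

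**What is split by group.** The quantitative analysis in A.3 and F.3 is descriptive, and no breakdown is mentioned. The only split in the Aim 3 analysis is qualitative: a coding team "will develop the code book for each group of interviews (patients and prosthetic care providers").

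**What the result is for.** C.4 says: "Evaluating the accuracy, comprehensibility, and usability of the DA with potential end-users will ensure that" the content is accurate, valuable to the decision and understandable to its target users. It adds that the findings will determine whether the DA goes forward to pilot testing. The closing paragraph of F.3 wants the DA tailored to both patients and providers.

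**The concern.** The 80% rule is the only numerical decision rule in the study, and it decides when revision ends. If it can be read in more than one way, the same scores can end testing or trigger another round, and the choice may be made after the scores are known.

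The second matter is what a pass can be taken to show. The plan wants a DA that suits two groups, but accuracy is one percentage over both together. A pooled 80% can coexist with a much lower figure in either group. Without a planned breakdown, nothing in the numerical results would show it.

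**Working it through.** The plan derives no sample size or power for Aim 3, so there is no figure of its own to reproduce. The check is a comparison of the texts followed by exact counting.

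**Step 1: the two stopping texts side by side.** The closing paragraph has two plausible readings: two rounds as an alternative to the threshold, or as a minimum in addition to it.

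| Lowest score so far | Main F.3 rule | Closing paragraph, alternative | Closing paragraph, minimum plus threshold |
|---|---|---|---|
| Above 80% in round 1 | stop | stop | second round |
| Exactly 80% in round 1 | stop | continue | continue |
| Exactly 80% in round 2 | stop | may stop | continue |
| Below 80% in round 2 | continue | may stop | continue |

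Every row contains a disagreement. Only the middle two depend on the cut-off; the first and last come from the two-round clause.

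**Step 2: how often exactly 80% can occur for accuracy.** Inputs: *a* patients and *b* providers, each 5 to 12 (B.1), so 8 × 8 = 64 compositions and *N* = *a* + *b* from 10 to 24. If all members respond, exactly 80% needs 0.8*N* to be a whole number, so *N* = 10, 15 or 20.

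- These totals arise in 1 + 6 + 5 = 12 of 64 compositions, including the smallest permitted group.
- The required count under 80% or more, against strictly above 80%, is 8 against 9 of 10, 12 against 13 of 15, and 16 against 17 of 20. At every other *N* the two cut-offs need the same count.
- Illustration, with an assumed true endorsement of 0.8 and independent members, at *N* = 10: P(at least 8) = 0.678 and P(at least 9) = 0.376. At 0.7 the pair is 0.383 and 0.149; at 0.9 it is 0.930 and 0.736.

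**Step 3: how low one group can be when pooled accuracy passes.** The smallest passing count is *k* = the smallest integer ≥ 0.8(*a* + *b*). If all *b* providers endorse, the lowest passing patient share is (*k* − *b*)/*a*.

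- 5 + 5: *k* = 8, so 3 of 5 (60%).
- 8 + 8: *k* = 13, so 5 of 8 (62.5%).
- 12 + 12: *k* = 20, so 8 of 12 (66.7%).
- 5 patients + 12 providers: *k* = 14, so 2 of 5 (40%).
- 12 patients + 5 providers: *k* = 14, so 9 of 12 (75%).

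Over all 64 compositions the share runs from 40% (5 patients with 10 to 12 providers) to 77.8% (7 of 9 patients with 5 providers). It is always below 80%, above 60% in 41 compositions and below 50% in 3. Exchanging the groups gives the same figures for providers.

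**Step 4: how often a by-group display would flag by chance.** Assume 90% true endorsement in both groups and independent members. With *i* and *j* the endorsing counts, the flag rate is P(*i* + *j* ≥ *k* and (*i*/*a* < 0.8 or *j*/*b* < 0.8)). Take 15 criteria: the five components in Table 1 of section 2.2 times three outcomes, assumed independent and all scored as shares of members. The chance of at least one flag is 1 − (1 − rate)^15.

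| Patients + providers | Rate per criterion | At least one of 15 |
|---|---|---|
| 5 + 5 | 0.09 | 0.74 |
| 12 + 12 | 0.12 | 0.86 |
| 8 + 8 | 0.27 | 0.99 |
| 9 + 9 | 0.30 | above 0.99 |

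**Step 5: Likert conversion.** On an assumed 5-point scale with every member rating 4, the score is 100% as the share rating 4 or 5, 4/5 = 80% as mean over maximum, and (4 − 1)/4 = 75% as a rescaled mean. The same ratings pass, tie or fail.

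**The case against.** The strongest reply is that this is descriptive alpha testing of a prototype ahead of a separate clinical pilot. Descriptive statistics do not exclude a by-group table. Interviews follow every round, are coded separately for patients and providers, and feed into revisions. The integration step and the audit trail already give dissent a route to be noticed. That stands: the missing breakdown is an unstated reporting detail, not an error. But the interviews are not part of the numerical rule, and nothing requires a low group score to be noted.

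Four stronger readings are tempting and are not supported.

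- A reader might infer that the two texts always give opposite decisions at exactly 80%. They do in round 1. Once two rounds are done, the closing paragraph can be read as permitting a stop, so the conflict then depends on the reading.
- A reader might infer that comprehensibility and usability are pooled in the same way. The documents give only a Likert scale per component, so this is possible but not documented.
- A reader might infer that a divided group is likely. The documents give no endorsement rates. Step 3 shows what is possible when one group is unanimous, and every probability above rests on assumed rates.
- A reader might infer that each group should have to reach 80%. On the assumptions of step 4, the chance that all 15 criteria pass would fall from 0.34 to 0.08 at 5 + 5, from 0.35 to 0.002 at 8 + 8 and from 0.26 to 0.03 at 12 + 12. The plan states no maximum number of rounds.

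It is also fair to say that the tie is narrow and that by-group flags will often be noise. Both limit the weight of the point.

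**Conclusion.** The concern holds in two parts of different weight.

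The stopping rule is wrong as written. The two texts differ at exactly 80%, and they differ more widely on whether two rounds add to the threshold or substitute for it. The cut-off conflict is confined, for accuracy with full response, to totals of 10, 15 or 20 members. The two-round ambiguity applies at any group size and to all three outcomes.

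The by-group breakdown is a cheap improvement, not the correction of an error. A pooled accuracy pass does not show that patients, or providers, reached 80%. This follows from the definition in A.3 and the sizes in B.1 by counting alone, given unanimity in the other group. How often it would happen cannot be learned from the documents. The unstated Likert conversion is a supporting clarification.

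**What to change.** **Stopping rule.** Use one rule in both places in F.3, with one cut-off. A cut-off of 80% or more agrees with the below-80% revision trigger already there. State whether two rounds are a minimum in addition to the threshold or an alternative to it. If an alternative, say plainly that testing may end after two rounds with a score below 80%. The edit costs a sentence; a two-round minimum costs a second round even when the first passes.

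**Reporting.** Add to F.3 wording such as: *For each component, accuracy, comprehensibility and usability are reported for patient members, provider members and all members, with counts and denominators. The conversion of Likert ratings to a percentage is fixed before round 1. Where either group is below 80% despite a pooled pass, the divergence is considered with that group's interview findings in the mixed-methods integration and recorded in the audit trail, and the DA is not described as endorsed by that group.* No per-group gate is proposed.

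The cost is a few sentences and one stratified table from data already collected. The downside is coarse percentages: one member is 20 points at 5 and about 8 points at 12. At least one chance flag is likely, so the text should add that a flag prompts discussion and is not evidence of a group difference.
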